8.3. Justification for the Study Design

Study has confirmed that early tumor response assessed by imaging evaluation can more accurately help to predict long-term survival in HCC patients treated with chemoembolization. Therefore, a 6-month objective tumor response rate (ORR) is used as the primary effectiveness endpoint. Since there is no report on 6-month ORR after cTACE in the Chinese population, this study selected 45% as the performance goal based on the 6-month ORR result in the cTACE controlled arm of a well-accepted international multicenter randomized controlled PRECISION V study. The PRECISION V study enrolled 212 subjects from 19 centers at France, Germany, Switzerland, Austria and Greece, The key inclusion criteria of this study is comparable with the PRECISION V study, including the BCLC staging (A/B), Child-Pugh score (A/B) and ECOG performance status (0/1).

9. Subject Selection

9.1. Study Population and Eligibility

Prior to being eligible for the STOPPER study, a subject must meet all of the inclusion criteria (Section 9.2) and none of the exclusion criteria (Section 9.3).

9.2. Inclusion Criteria

Subjects may be enrolled in the study if they meet all of the following criteria:

- 1. Patient is able to provide informed consent and must sign the Institutional Review Board/Ethics Committee (IRB/EC) approved Informed Consent Form.
- 2. Male or female of age \geq 18 and \leq 75 years.
- 3. Confirmed diagnosis of HCC according to the diagnostic criteria included in the management guideline issued by China's Ministry of Health in 2017.
- 4. HCC is diagnosed for the first time or recurrence of tumor after surgical or ablation treatment
- 5. Single tumor less than 7cm in diameter or multiple tumors with less than 3 lesions with >1cm in diameter, individual diameter <7cm and less than 10cm in total diameter.
- 6. No previous chemotherapy, radiotherapy or transarterial embolization (with or without chemotherapy) for HCC
- 7. Preserved liver function (Child-Pugh A or B7).
- 8. ECOG Performance Status 0 or 1.

9.3. Exclusion Criteria

Subjects will be excluded for any of the following reasons:

- 1. Presence of vascular invasion or extra-hepatic spread of disease, or diffuse HCC, defined as >50% liver involvement, or arteriovenuous fistula
- 2. Macrovascular invasion of main or primary branches of portal vein at entry into the study
- 3. Any contraindication for TACE treatment
- 4. Any contraindication for Epirubicin administration
- 5. Advanced liver disease (bilirubin levels >2 mg/dl, AST or ALT >5 times upper limit of normal)
- 6. Renal failure or insufficient renal function (Creatinine levels >2 mg/dl)
- 7. Subject unable to receive MRI examination
- 8. Pregnant or breast feeding woman, or plan to become pregnant during treatment or within 12 months of treatment
- 9. Couldn't commit reliable birth control measures during treatment or within 12 months of treatment
- 10. Subject is participating other investigational drug or device clinical trial within 30 dys of signing the informed consent
- 11. Subject is not suitable to participate in the study as judged by investigator

Form/Template 90702637 Rev/Ver AH STOPPER China Protocol, 92040370 Rev/Ver AD Page 23 of 59

10. Subject Accountability

10.1. Enrollment

Confirmed HCC patient, who has signed the IRB/IEC-approved study ICF, and has met all inclusion criteria and none of the exclusion criteria, will be considered eligible to be enrolled in the trial. If the subject does not meet all of the inclusion criteria or meets any of the exclusion criteria, it will be regarded as screening failure, and the subject will not be enrolled in the study and receive investigational device, and will not be followed according to the study protocol. All qualified subjects will receive DEB-TACE treatment with Tandem. The enrollment timepoint will be based on subject receiving initial transcatheter arterial chemoembolization treatment with Tandem Microspheres loaded with Epirubicin

10.2. Withdrawal

All enrolled patients should be documented (including those withdraw from the study or lost to follow-up). The reason for withdrawal will be recorded in all cases of withdrawal. If such withdrawal is due to problems related to investigational device safety or performance, the investigator shall ask for the subject's permission to continue to follow his/her status/condition.

10.3. Enrollment Control

A minimum of 98 enrolled subjects are needed to adequately assess the primary endpoint at 6 months after initial treatment. To account for attrition, minimum enrolment shall be 109 subjects, assuming a maximum attrition of 10% for all reasons at 6 months. The enrollment cap for each study site is 25% of total enrolled subjects, which is 27 subjects. The study recruitment will stop when 109 qualified subjects completed enrollment.

11. Study Methods

11.1. Data Collection

The data collection plan is shown in Table 11.1. The follow-up window is 14 days.

Form/Template 90702637 Rev/Ver AH STOPPER China Protocol, 92040370 Rev/Ver AC Page 24 of 59

Table 11.1 Baseline and Follow-up Evaluation Plan

Table 11.1 Dasenne and Ponow-up Evaluation Flan											
	Screening/Baseline	Treatment initiation	30-day Follow-up post initial treatment	30-day assessment post 2 nd treatment (if necessary)	3-month Follow-up post initial treatment	6-month Follow-up post initial treatment	12-month Follow- up post initial treatment				
	Within 14 days of treatment	Day 0	$30\!\pm\!14$ days		91±14 days	183±14 days	365±14 days				
Informed Consent	\checkmark										
Inclusion/Exclusion	√	$\sqrt{}$									
Demographics (including date of birth, gender and ethnicity)	√										
Cancer and treatment history											
Physical examination	√		V	V	V	√	√				
Child-Pugh Score	√		V	V	V		√				
ECG	√				V						
Laboratory tests *	√		V	V	V		√				
Pregnancy Test # (if applicable)	V										
Imaging and tumor measurement	$\sqrt{}$		$\sqrt{}$	$\sqrt{}$	$\sqrt{}$	$\sqrt{}$	\checkmark				
Chest plain CT	√		$\sqrt{}$	$\sqrt{}$	$\sqrt{}$	$\sqrt{}$	$\sqrt{}$				
ECOG performance status	√		√	√	√	√	V				
Concomitant Medication post treatment	√	$\sqrt{}$	√		√	√	√				
Adverse Events and device failure assessment		$\sqrt{}$	$\sqrt{}$		V	V	V				
Vital status			$\sqrt{}$								

^{*} Baseline Laboratory Tests include: complete blood count (WBC, RBC, Hb, PLT), Blood biochemistry (TP, ALB, TBIL, IBIL), Liver function tests (ALT, AST, ALP), Renal function tests (BUN, Cr), Anticoagulation (PT, APTT, INR), Electrolyte (K, Na, CI, Ca), hepatitis B panel and anti-HCV, AFP

All laboratory tests must be completed within 14 days of study treatment, childbearing woman should complete serum and/or urine pregnant test within 7 days of treatment

[#] Serum and/or urine pregnant test

11.2. Study Candidate Screening

Screening process will be performed to confirmed primary HCC subjects based on inclusion and exclusion criteria. Subjects who are suitable for DEB-TACE will be informed about the study and will be asked to sign the informed consent form (ICF) before participating in any screening procedure. After signing the ICF, the subject will receive a screening number and will be documented in a screening log. Each clinical investigator must keep a log of all screened subjects, including both eligible and non-eligible subjects (screening failures). The screening log will be kept by each study center.

11.3. Informed Consent

Before the initiation of the screening process, subjects who meet the clinical inclusion criteria will be asked to sign the IRB/IEC-approved study ICF. Subjects must be given ample time to review ICF and have questions answered before signing ICF.

Study personnel should explain to the subject that even if the subject agrees to participate in the trial and signs the ICF, the pre-treatment tests including pre-embolization radiography may demonstrate that the subject is not a suitable candidate for the clinical trial.

11.4. Screening/Baseline Survey

The procedures to be completed within 14 days prior to treatment are as follows. Among them hepatitis B markers, HBV-DNA (if necessary), anti-HCV and imaging test result within 10 days of IC signature as well as other serum tests within 5 days of IC signature at the same research center can be accepted for screening and baseline survey data.

- Obtain written subject informed consent.
- Obtain detailed documentation of cancer history with treatments and outcomes.
- Demographics.
- Physical Examination (height, weight, pulse, blood pressure)
- Child-Pugh Score
- ECOG performance status
- Plain and Enhanced MRI to assess intrahepatic tumor
- Chest plain CT and other tests (if necessary) to exclude extrahepatic lesion
- ECG.
- Pregnancy Test: If female is of child bearing potential, non-pregnancy to be confirmed with urine or serum test.

Laboratory tests to be done at baseline:

- Complete Blood Count (WBC, RBC, Hb, PLT)
- Blood biochemistry (TP, ALB, TBIL, IBIL)
- Liver function tests (ALT, AST, ALP)
- Renal function tests (BUN, Cr)

Form/Template 90702637 Rev/Ver AH STOPPER China Protocol, 92040370 Rev/Ver AD Page 26 of 59

- Anticoagulation (PT, APTT, INR)
- Electrolyte (K, Na, CI, Ca)
- Hepatitis B panel and anti-HCV (test HBV-DNA if HBsAg positive)
- AFP

MRI Imaging to be done at baseline and during the study treatment phase:

MRI imaging system should be ensured during all assessments for each subject with the same technique being used throughout the treatment period for evaluating the lesions. Scanning sequence include coronal T2WI, transect T2WI, T1WI, DWI, enhanced scan using 3D T1WI. Tumor measurements will be assessed at Core laboratory. Sites should send the imaging for review. The target lesions must meet all of the following according to the mRECIST for HCC Guideline: The lesion can be measured in at least one dimension \geq 1 cm; The lesion appears to be suitable for accurate and repeat measurement; The lesion shows intratumoral arterial enhancement.

Test to be done at baseline and during the study treatment phase to exclude extrahepatic metastasis

Perform chest CT test to exclude lung metastasis. Other tests could also be done if necessary to exclude extrahepatic metastasis.

11.5. Initial Tandem Treatment

The end of initial treatment is defined as the completion of the first DEB-TACE with Tandem microspheres. Post-treatment evaluation will be conducted by site after each DEB-TACE procedure to determine the need for next session, and complete the next embolization treatment within 14 days of assessment if necessary. A maximum of 4 treatment may be performed to the subject during the study. If a subject received 4 treatments, no 30-day post treatment assessment will be conducted, and the subject will continue to receive 6-month post treatment follow-up. See the flow chart for detailed post-treatment evaluation and follow-up plan on subjects receiving different times of DEB-TACE treatments. The following should be completed after each DEB-TACE procedure:

- Record the procedural date/time, microsphere lot #, microsphere size and volume, microcatheter used,epirubicin manufacturer, epirubicin lot #, epirubicin dose, contrast type and volume, infusion volume, lesion(s) treated and flow characteristic.
- AE and concomitant medicine used during DEB-TACE

•

11.6. 30-day Clinical Follow-up Post Initial Treatment

• Physical examination (weight, pulse, blood pressure)

- ECOG and Child-Pugh scores
- Lab tests (Complete Blood Count, blood biochemistry, liver and renal functions, blood coagulation function, electrolyte, AFP,)
- Enhanced MRI to assess the tumor response and Chest plain CT
- Concomitant medications since last visit
- Record of all adverse events that occurred from last subject contact

Note: If the 30-day evaluation post initial treatment indicates complete response of the target lesion, the subject will received scheduled 3, 6 and 12-month follow; If the 2nd treatment is needed, it will be completed within 14 days of assessment, and a 30-day evaluation will be conducted after the 2nd treatment; If the 3rd treatment is needed, it will be completed within 14 days of assessment, and the subject will receive the post-treatment evaluation and 3-month follow-up at the same time.

11.7. 3-month (91 \pm 14 days) Clinical Follow-up Post Initial Treatment

- Physical examination (weight, pulse, blood pressure)
- ECOG and Child-Pugh scores
- Lab tests (Complete Blood Count, blood biochemistry, liver and renal functions, blood coagulation function, electrolyte, AFP)
- ECG
- Enhanced MRI for tumor response and Chest plain CT
- Concomitant medications since last visit
- Record of all adverse events that occurred from last subject contact

11.8. 6-month (183 ± 14 days) Clinical Follow-up Post Initial Treatment

- Physical examination (weight, pulse, blood pressure)
- ECOG and Child-Pugh scores
- Lab tests (Complete Blood Count, blood biochemistry, liver and renal functions, blood coagulation function, AFP)
- Enhanced MRI for tumor response and Chest plain CT
- Concomitant medications since last visit
- Record of all adverse events that occurred from last subject contact
- Vital status

11.9. 12-month (365 \pm 14 天) Clinical Follow-up Post Initial Treatment

- Physical examination
- ECOG and Child-Pugh scores

Form/Template 90702637 Rev/Ver AH STOPPER China Protocol, 92040370 Rev/Ver AD Page 28 of 59

- Lab tests (Complete Blood Count, blood coagulation function, AFP, liver and renal functions)
- Enhanced MRI for tumor response and Chest plain CT
- Concomitant medications since last visit
- Record of all adverse events that occurred from last subject contact
- Vital status

11.10. Study Completion

All subjects who completed the 12 months follow-up, or withdrawn (due to death or loss to follow-up), or will be treated as study termination. Any adverse events occurred afterwards will be addressed by the physician per standard treatment.

Subjects may withdraw their consent and discontinue participation in the clinical study at any time, for any reason, without prejudice to further treatment. If a subject no longer wants to receive study treatment, but is willing to come for follow-up appointments, the subject's request should be honored, if possible.

If for any reason a subject is withdrawn or terminated before completing the study, the reasons for withdrawal or termination must be documented.

If a subject discontinues treatment due to an adverse event or clinical laboratory abnormality, the subject should be followed-up until the event resolves or the subject stabilized.

12. Statistical Considerations

12.1. Endpoints

12.1.1. Primary Endpoint

The primary endpoint of the study is 6-month ORR. Objective tumor response will be assessed by The European Association for the Study of the Liver (EASL) Response Evaluation Criteria in Solid Tumors and a modified Response Evaluation Criteria in Solid Tumors (mRECIST¹⁹). The mRECIST criteria can be more accurate to predict long-term survival in HCC subjects treated with chemoembolization²⁰. The subject achieves complete response (CR) or partial response (PR) will be regarded as a responder. A subject without tumor assessment after the initiation of the treatment will be regarded as a missing data.

12.1.1.1. Hypotheses

The primary hypotheses is the 6-month ORR in subjects treated with transcatheter arterial chemoembolization with drug-loaded Tandem Microspheres exceeds the PG under a one-sided significance level of 2.5%. The PG development is based on PRECISION V, an international multicenter study. The ORR will be assessed based on the EASL criteria.

The null (H_0) and the alternative (H_1) hypotheses for the primary effectiveness endpoint are as follows:

 H_0 : $P_e \le PG$ (not met)

 $H_1: P_e > PG \text{ (met)}$

where P_e is the expected 6-month ORR (%).

12.1.1.2. Sample Size

The overall sample size is driven by the primary effectiveness endpoint. Approximately 109 subjects are planned to be enrolled in the study. The sample size justification is based on the following assumptions.

- Power $\geq 85\%$
- One-sided significance level = 2.5% (alpha)
- PG for 6-month ORR = 45%
- Expected 6-month ORR = 60%
- A minimum of 98 evaluable subjects are required for 6-month assessment
- Attrition rate = 10% (loss to follow-up in 6 months)
- A sample size of 109 subjects will be enrolled in the study

12.1.1.3. Statistical Methods

A normal approximation test (e.g. Chi-Square Test) will be used to assess the superiority to the PG.

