12.1.1.4. Success Criteria

The test device will be concluded to be superior to the PG if the one-sided 97.5% lower confidence bound for the observed performance in 6-month ORR is greater than PG.

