7.2 SAS Codes for Chi-Square Test

The confidence intervals and the Chi-Square test p-value can be produced by the following SAS code.

```
proc freq data=;
  tables xx/binomial(p=) alpha=;
```

run;

For example, the worst case scenario in the PG testing of the primary effectiveness hypotheses is used for the exercise. A dummy frequency table is coded as below.

```
%let total=98; %let yes=54; %let no=&total.-&yes.; data dsn1; yn=1; wgt=&yes.; output; yn=0; wgt=&no.; output; run;
```

A list of SAS codes for Binomial and Chi-Square method is used for PG=45% and 95% confidence limits to control the Type I error under one-sided 2.5% (i.e. two-sided 5%).

```
proc freq data=dsn1 order=data;
  tables yn/ binomial(p=.45) alpha=.05;
  weight wgt;
run;
```

The SAS output for the worst case scenario is presented below.

Binomial Proportion yn = 1

```
Proportion
                           0.5510
ASE
                           0.0502
95% Lower Conf Limit
                           0.4525
95% Upper Conf Limit
                           0.6495
Exact Conf Limits
95% Lower Conf Limit
                           0.4472
95% Upper Conf Limit
                          0.6517
 Test of HO: Proportion = 0.45
ASE under HO
                           0.0503
                           2.0102
One-sided Pr > Z
                           0.0222
Two-sided Pr > |Z|
                           0.0444
        Sample Size = 98
```

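### At 98 evaluable subjects the normal-approximation rule carries an exact one-sided error of 2.85%, not 2.5%, and the type of confidence bound that decides success is not named

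*Protocol*

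**What the plan says.** Protocol 12.1.1.2 sets out the design: "One-sided significance level = 2.5% (alpha"), power of at least 85%, a performance goal of 45%, an expected ORR of 60%, and "A minimum of 98 evaluable subjects are required for 6-month assessment". Allowing 10% attrition, 109 are enrolled.

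Protocol 12.1.1.3 names the method: "A normal approximation test (e.g. Chi-Square Test) will be used to assess the superiority to the PG". SAP 3.1.4 repeats it. Protocol 12.1.1.4 declares success "if the one-sided 97.5% lower confidence bound for the observed performance in 6-month ORR is greater than PG", without saying whether the bound is Wald, score or exact.

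SAP 7.2 gives PROC FREQ code and output for 54 responders of 98, and says the settings are chosen "to control the Type I error under one-sided 2.5"%. The output lists an asymptotic lower limit of 0.4525, then, under "Exact Conf Limits", a lower limit of 0.4472, then Z = 2.0102 with one-sided p = 0.0222.

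Two other SAP statements bear on the same rule. Section 3.1.5 gives 52 of 98 as the minimum number of responders. Section 3.3 compares the lower bound with zero, not with the performance goal.

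**The concern.** This is the trial's only hypothesis test, made in a single arm against a fixed goal, so the claim of effectiveness rests on one threshold count. With about 100 binary outcomes, a normal-approximation threshold can sit one responder too low to hold the nominal error. SAP 7.2 says error is controlled at 2.5%, so this can be checked at the SAP's own example. Because the bound is unnamed and the output prints two limits on opposite sides of 45%, a borderline result could also be disputed after the data are known.

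**Working it through.** **Inputs** (Protocol 12.1.1.2): p0 = 0.45, p1 = 0.60, one-sided alpha = 0.025 (z = 1.960), power 85% (z = 1.036).

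**1. The plan's sample size.** One-sample normal approximation, null variance for alpha and alternative variance for power:

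n = [(1.960 × √(0.45 × 0.55) + 1.036 × √(0.60 × 0.40)) / 0.15]² = 97.72, rounded up to 98.

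Approximate power at 98 is 85.1%. Enrolment is 98 / 0.90 = 108.9, rounded up to 109. Both stated figures reproduce.

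**2. The SAP example.** For 54/98 = 0.5510:

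- Z = (0.5510 − 0.45) / √(0.45 × 0.55 / 98) = 2.010, one-sided p = 0.0222.
- Wald lower limit: 0.5510 − 1.960 × √(0.5510 × 0.4490 / 98) = 0.4525.
- Exact (Clopper-Pearson) lower limit: 0.4472.

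All match the SAP output.

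**3. Thresholds at n = 98, with exact binomial error and power.** Error is P(X ≥ x | 98, 0.45); power is P(X ≥ x | 98, 0.60).

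| Responders | Z | Wald lower limit | Exact lower limit | Exact one-sided error | Power at 60% |
|---|---|---|---|---|---|
| 52 | 1.604 | 0.4318 | 0.4271 | 6.68% | 93.3% |
| 53 | 1.807 | 0.4422 | 0.4371 | 4.44% | 90.2% |
| 54 | 2.010 | 0.4525 | 0.4472 | 2.85% | 86.3% |
| 55 | 2.213 | 0.4630 | 0.4573 | 1.76% | 81.3% |

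The score test and the Wald bound both first pass at 54; the exact bound first passes at 55. The 52 of SAP 3.1.5 passes under none of the three.

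**4. Other evaluable numbers.** The final number depends on attrition, so the same enumeration was run around 98. Score and Wald share a threshold at every n from 88 to 111.

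| n | Normal rule: threshold, error, power | Exact rule: threshold, error, power |
|---|---|---|
| 98 | 54, 2.85%, 86.3% | 55, 1.76%, 81.3% |
| 99 | 55, 2.25%, 84.3% | same |
| 103 | 57, 2.25%, 85.7% | same |
| 104 | 57, 2.82%, 88.1% | 58, 1.77%, 83.7% |
| 105 | 58, 2.24%, 86.3% | same |
| 106 | 58, 2.82%, 88.6% | 59, 1.77%, 84.4% |
| 107 | 59, 2.24%, 86.9% | same |
| 108 | 59, 2.81%, 89.2% | 60, 1.77%, 85.1% |
| 109 | 60, 2.24%, 87.5% | same |

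At every even n from 90 to 108 the normal rule's error is 2.81% to 2.86%. At every odd n from 89 to 111 the rules coincide and the error is 2.23% to 2.25%. Exact-rule power is at least 85% at 103, 105 and every n from 107 to 111, but not at 104 or 106.

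**The case against.** The strongest reply is that the plan does name its method. Both synopses, Protocol 12.1.1.3 and SAP 3.1.4 specify a normal approximation, and SAP 7.2 is headed as chi-square code. The score test and its Wald counterpart agree at every evaluable number checked, and no section makes the exact limit the decision rule. Nominal alpha for such a test is approximate by nature, 0.35 points is small, and under the declared rule the stated power holds at 98.

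Much of this stands. A reader might infer that the sample size is wrong, that the trial is underpowered as planned, or that the two printed limits are equally valid readings of the rule. The documents do not support these. The sample size reproduces; 81.3% is the power under a rule the plan did not choose; and the natural reading of the named method is the asymptotic limit. Nor is the excess error general: with all 109 subjects evaluable it vanishes.

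What does not fall away is that SAP 7.2 claims control at 2.5% for an example whose exact error is 2.85%, and that the success criterion leaves the bound unnamed. The SAP also gives 52/98 in one section, uses 54/98 in another, and compares the bound with zero in a third, so its text does not settle the threshold for the reader.

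**Conclusion.** The point holds as one of specification and disclosure, not as a miscalculation. At the planned 98 evaluable, the normal rule exceeds the stated one-sided error by 0.35 points (2.85% against 2.5%), with power of 86.3%. The exact rule holds the error at 1.76% but has power of 81.3%. So no threshold at n = 98 delivers both an exact error of at most 2.5% and power of at least 85%. The two rules differ by one responder at even evaluable numbers and not at all at odd ones.

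This rests on independent binary outcomes, a true ORR of exactly 45% for the error and 60% for power, and a fixed evaluable number. The practical effect is confined to a result on the threshold, but that is the situation a pre-specified rule has to settle.

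**What to change.** In Protocol 12.1.1.3 and 12.1.1.4 and in SAP 3.1.4, 3.3 and 7.2, name the exact (Clopper-Pearson) one-sided 97.5% lower bound, compared with the 45% goal at the actual evaluable number, as the decision rule. The existing SAS code already prints it. In the same edit:

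- replace the 52/98 minimum in SAP 3.1.5 and the 54/98 example in SAP 7.2 with 55/98;
- change the comparison with zero in SAP 3.3 to the performance goal;
- restate power as 81.3% at 98 evaluable and 87.5% at 109, noting that it is 83.7% at 104 and 84.4% at 106.

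If the normal rule is kept, say explicitly that the bound is asymptotic, give 54/98 as the threshold in both SAP sections, make the same correction in SAP 3.3, and state the true one-sided error: 2.85% at 98, about 2.2% at odd numbers and 2.8% to 2.9% at even numbers.

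The cost of the exact rule is one more responder at even evaluable numbers and a less favourable stated power. It needs no extra patients, provided 81.3% at 98 is accepted. Keeping at least 85% whatever the parity would need 107 evaluable, which at 10% attrition means 107 / 0.90 = 118.9, or 119 enrolled.
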